## 8 STUDY PROCEDURES

### 8.1 Written Informed Consent

The provided written informed consent form (ICF) must be signed before any protocol specific procedures and assessments can be performed. A copy of the signed ICF will be given to the subject and a copy should be filed in the medical record. The original ICF should be kept on file with the study reports. Standard of care evaluations performed as part of the subject's routine treatment prior to signing the ICF can be used if they were conducted within the timeframe of the screening period. Refer to [Section 13.8](#) for further information.

## 8.2 Subject Registration

Centralized registration of subjects will be completed according to a process defined by the Sponsor. Eligible subjects are to be enrolled and assigned a unique study identification number before the planned intratumoral Ad-RTS-hIL-12 injection. Once assigned, a subject's identification number will not be reused.

## 8.3 Description of Procedures and Observations

Screening assessments must be performed within 28 days prior to the Ad-RTS-hIL-12 injection. Any screening tests, exams or procedures outside of this range may be repeated at the investigator's discretion. All study visits must be completed as described in the protocol while subjects are taking veledimex capsules.

### 8.3.1 *Study Tests, Exams and Procedures*

#### 8.3.1.1 Demographics, Medical and Cancer History, and Concomitant Medications

Each subject's complete medical history will be documented during screening, including demographic information, relevant medical history, current primary cancer diagnosis, and prior cancer treatments (chemo- and immunotherapies, radiation therapy, surgeries). In addition, concomitant medications, including blood products, vitamins, and other supplements received during the screening period (28 days) prior to initiating study treatment will be recorded. Concomitant medications will continue to be collected through the Initial Follow-up Period (Week 12).

#### 8.3.1.2 Physical Examinations

A physical examination (PE) will include examination of the subject's general appearance, and the following organ systems: heart, lung, head and neck, abdomen, skin, and extremities.

#### 8.3.1.3 Vital Signs, Height and Weight

Vital signs will include blood pressure, pulse rate, temperature, and respiration rate. Subject's blood pressure is to be monitored closely, [REDACTED] for 72 hours after administration of Ad-RTS-hIL-12. Assessment of vital signs is required prior to injection of Ad-RTS-hIL-12, and prior to veledimex dosing on day 1. The assessment of vital signs on day 3 and 7 should be performed prior to administration of veledimex.

Height and weight will be measured and recorded according to [Schedule of Study Procedures](#).

#### 8.3.1.4 ECOG Performance Status

See [Appendix 16.1](#). Subjects will need to have ECOG performance status of 0 or 1 to be eligible for the study.

#### **8.3.1.5      Pregnancy Testing**

Females of childbearing potential will have a serum pregnancy test at the screening visit within 14 days of dosing and a urine pregnancy test at Day 1. The pregnancy test must be negative prior to administration of veledimex and injection of Ad-RTS-hIL-12. A serum pregnancy test should be completed on Day 1 if the urine pregnancy test is positive.

#### **8.3.1.6      Monitoring of Adverse Events**

Monitoring and recording of AEs and SAEs will be conducted throughout the study. AEs and SAEs from the signing of informed consent until the end of week 6 will be collected and entered into the case report forms (CRFs). After Week 6, only SAEs suspected of being related to Ad-RTS-hIL12 immunotherapy will be collected.

Adverse events will be recorded on the CRFs using NCI CTCAE v.4.03 criteria. MedDRA will be used for evaluating AEs. Definitions, documentation, and reporting procedures for adverse events are described in detail in [Section 10](#).

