### Study Assessments and Criteria for Evaluation

#### Safety Assessments

Safety parameters will include AEs, SAEs, physical examinations (PEs), ECGs, vital signs, clinical laboratory evaluations, medical history, and prior/concomitant medications. All AEs/SAEs will be collected from the signing of informed consent until the end of Week 12. Subjects who experience drug-related Grade 3 AEs during the first 7 days of oral dosing with veledimex will interrupt/discontinue further dosing at the discretion of the investigator. Subjects who experience drug-related Grade 4 AEs during the first 7 days of oral dosing with veledimex will discontinue therapy. The decision as to whether subjects who experience severe or serious treatment-related adverse events will remain on treatment will be made by the investigator in conjunction with the Sponsor medical monitor.

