- q. If radiographic PD is recorded at 6 weeks, PD must be confirmed 4 weeks later. In cases of slow tumor growth, the investigator may wait until confirmation of the PD at 12 weeks to resume chemotherapy. In cases of unequivocal progression, the investigator may resume chemotherapy prior to 12 weeks.
- r. Subjects who have SD or better at Week 12 will continue into the long-term follow-up period where imaging should continue per the schedule until a radiographic response of PD is confirmed.
- s. Biopsy on Day 1 is to be taken 3 hours  $\pm$  3 hours after administration of veledimex and prior to injection of Ad-RTS-hIL-12.
- t. After Week 6, only SAEs suspected of being related to investigational product will be collected.
- u. The follow-up visits can be performed within  $\pm$  1 week.

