For subjects with HER2- disease, the Ad-RTS-hIL-12 immunotherapy is intended to be given as a chemotherapy holiday, for example, to avoid intolerable or undesirable toxicity of the standard therapy. Ad-RTS-hIL-12 immunotherapy must be started within 4 weeks of stopping the pre-study standard chemotherapy.

Subjects with HER2+ disease will receive the Ad-RTS-hIL-12 immunotherapy in conjunction with first-, second-, or third-line anti-HER2 antibody therapy, i.e., subjects may continue anti-HER2-directed antibody therapy during the study period. Anti-HER2 antibody therapy will be administered according to the manufacturer's recommendations. Subjects with HER2+ breast cancer who continue the anti-HER2 antibody therapy need to recover from any anti-HER2 related AE/SAE, i.e., the event must have resolved to Grade 1 or baseline, before starting Ad-RTS-hIL-12 immunotherapy.

The Ad-RTS-hIL-12 immunotherapy cycle is a 21-day cycle comprised of investigational product administration on days 1 through 7 followed by rest on days 8 through 21. On day 1, enrolled subjects will receive the first dose of veledimex followed 3 hours  $\pm$  3 hours later by an intratumoral injection of Ad-RTS-hIL-12. The veledimex will continue to be given once daily on days 2 through 7 (see [Section 5](#) below, for details).

A safety review committee (SRC) will convene after every 5th subject with HER2- disease have completed the Ad-RTS-hIL-12 immunotherapy cycle (i.e., after each subject has completed 21 days on study). The SRC will also convene after the first 5 subjects with HER2+ disease have completed the Ad-RTS-hIL-12 immunotherapy cycle. The SRC will consist of the investigator, medical monitor, and other appropriate Sponsor representatives. The SRC will review all available safety information (AEs/SAEs, laboratory parameter data, ECG etc.). Tolerability will be evaluated separately for subjects with HER2- and HER2+ disease.

The safety evaluation will be based on the occurrence of related, treatment refractory Grade 3 and 4 AEs within 21 days following the start of Ad-RTS-hIL-12 immunotherapy. A post-treatment safety assessment visit will be conducted on Day 21.

The primary endpoint is safety/tolerability, defined as the proportion of patients who are able to complete 12 weeks on study without a Grade 3 or higher toxicity as defined by [Section 12.4.2](#).

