## 10.6 Documenting Adverse Events

All AEs (including SAEs) are to be accurately recorded on the Adverse Event page of the subject's electronic CRF from the time the subject signs the informed consent through the Follow-up Period. Each event will be assessed for serious criteria, severity, and causality (see [Section 10.5](#)). The date of onset, as well as the duration of the event will be recorded. In addition, treatments provided to the subject, actions taken with the investigational product, and the outcome of the AE will also be noted.

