### **Required Follow-up for Adverse Events**

All AEs and SAEs will be collected from the signing of the ICF through Week 6. After Week 6, only SAEs suspected of being related to investigational product will be collected. Follow up information for ongoing SAEs will be requested by the Sponsor until one of the following occurs:

- The event resolves
- The event returns to baseline, if a baseline value is available
- The event stabilizes (following consultation and agreement by the medical monitor)
- The event can be attributed to factors other than the investigational product or other than study procedure

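### Adverse event collection stops at Week 6, Week 12 or the follow-up period depending on the section; if the primary tolerability endpoint runs 12 weeks, the Week 6 rule leaves recorded tolerability equal to or above the truth

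*Protocol*

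**What the plan says.** **Endpoint.** Section 3.1 gives the primary endpoint in these words: "the proportion of patients who are able to complete 12 weeks on study without a Grade 3 or higher toxicity as defined by". The cross-reference that completes the sentence is to Section 12.4.2; the synopsis gives the same definition. Section 3.1 also bases the safety evaluation on "related, treatment refractory Grade 3 and 4 AEs within 21 days following the start of Ad-RTS-hIL-12 immunotherapy".

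**Collection of adverse events.** The current text, leaving the amendment tables aside, gives these instructions:

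- *Week 6.* Section 8.3.1.6 collects all AEs and SAEs to the end of Week 6 and then says "After Week 6, only SAEs suspected of being related to Ad-RTS-hIL12 immunotherapy will be collected". Footnote t of the Schedule of Study Procedures says "After Week 6, only SAEs suspected of being related to investigational product will be collected". Section 10.9 says "All AEs and SAEs will be collected from the signing of the ICF through Week 6".
- *Week 12.* The synopsis, under Safety Assessments, says "All AEs/SAEs will be collected from the signing of informed consent until the end of Week 12".
- *Follow-up.* Section 10.6 has all AEs recorded on the electronic CRF "from the time the subject signs the informed consent through the Follow-up Period". The schedule has an initial follow-up period (to Week 12) and a long-term one (to Week 48), and Section 10.6 does not say which it means.
- *General.* Section 8.3.1.6 itself opens with "Monitoring and recording of AEs and SAEs will be conducted throughout the study", and Section 8.4.9 lists adverse events among the Week 12 assessments.

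**Section 12.4.2.** Treatment-emergent events are counted to the end of a safety evaluation period that the section treats as already defined, but Section 12 defines none. Its only Grade 3 criterion is the stopping-rule event: a related, treatment-refractory AE of Grade 3 or 4.

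**The concern.** A site cannot follow the synopsis and Section 10.9 together, and the data at issue feed the primary endpoint. The conflict also has a direction. A subject who completes Week 12 and whose only qualifying event is non-serious and starts after Week 6 is not entered as a toxicity under the Week 6 rule, so she counts as a tolerability success. If the endpoint counts toxicity regardless of relationship, unrelated SAEs after Week 6 are lost as well. Nothing in the rule turns a success into a failure, so errors cannot cancel.

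Such an event may still appear in source records, because monitoring continues and Week 12 lists adverse events. Finding it there afterwards is less reliable than collecting it prospectively, and no analysis plan can restore data that the CRF was told not to hold.

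**Working it through.** **1. The protocol's own figure.** The only sample-size figure is the exact 95% confidence interval half-width of 0.16 for the progression rate at N = 40 (Section 12.2). The Clopper-Pearson interval is widest at 20 of 40: 0.338 to 0.662, half-width 0.162. The figure reproduces. It concerns progression, and nothing below depends on it.

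**2. Which reading of the endpoint is exposed.**

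- *Related, treatment-refractory Grade 3 or 4 events within 21 days:* the window closes at Day 21, before Day 42. Missed events = 0.
- *A 6-week window:* the Week 6 rule covers it. Missed events = 0.
- *A 12-week window, related events only:* related SAEs are still collected; related non-serious Grade 3 or higher events in Weeks 6 to 12 are not.
- *A 12-week window, any relationship:* unrelated SAEs in Weeks 6 to 12 are also missed.

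Subjects who die or leave before Week 12 fail the completion requirement anyway, so they cannot be misclassified. The 21-day stopping rule is unaffected.

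**3. Direction on the 12-week readings.** Among subjects who complete Week 12, let p be the probability of a qualifying event by Week 6, q the probability of a first one in Weeks 6 to 12 given none before, and s the share of those late events that is still captured.

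- True tolerability = (1 − p)(1 − q)
- Recorded tolerability = (1 − p)(1 − qs)
- Recorded minus true = (1 − p) q (1 − s) ≥ 0

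The difference is zero only if there are no first late events or all of them are captured (or if p = 1). A patient-level simulation of 20,000 trials of 40, with non-completers counted as failures in both versions, agrees: recorded tolerability was below the truth in 0 trials and equal to it in 6,599.

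**4. Size.** The documents give neither q nor s, so the bias cannot be computed from them. An illustration on assumed values only: p = 25%, q = 10% and s = 50% gives 0.75 × 0.10 × 0.50 = 3.75 points, or 1.5 of 40 subjects if all complete. With p still 25%, q from 5% to 20% and s from 0 to 75%, the range is 0.9 to 15.0 points. The conclusion does not use these numbers.

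**5. What does follow from the documents.**

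- Time without full collection: 84 − 42 = 42 days; 42/84 = 50%.
- Footnote u allows follow-up visits to move by 1 week: Week 6 at Day 35 to 49, Week 12 at Day 77 to 91. If the cut-off moves with the Week 6 visit, the gap runs from 77 − 49 = 28 to 91 − 35 = 56 days. If the cut-off stays at Day 42 and only the Week 12 visit moves, it runs from 77 − 42 = 35 to 91 − 42 = 49 days.
- Effect of one misclassified subject: 1/40 = 2.5 points overall. Tolerability is evaluated separately by HER2 status, with up to 8 HER2+ subjects (Section 4.3). At that ceiling, the step is 1/32 = 3.1 points for HER2− and 1/8 = 12.5 points for HER2+.

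**The case against.** The strongest reply is that the protocol's own cross-reference points to the reading with no bias. The endpoint defers to Section 12.4.2, whose only Grade 3 criterion is the stopping-rule event, and Section 3.1 evaluates that event over 21 days. On this view, 12 weeks adds only a completion requirement, and Week 6 collection is ample. This is a fair reading but not an established one, because Section 12.4.2 gives the primary endpoint no window. It stands as a condition on the bias; it does not reconcile the collection instructions.

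Second, few events are likely to be lost. Dosing is confined to Days 1 to 7. Haematology and chemistry are drawn at Week 12, and laboratory values, vital signs and examinations are summarised by visit, so a Grade 3 laboratory value present at that visit stays in the data. If the Section 12.4.2 criterion were applied over 12 weeks, a lost event would also have to be related and treatment-refractory. All of this stands and makes a modest bias more likely. It does not reverse the sign, and transient events between visits could still be lost.

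Third, the per-subject steps are simply 1/n, and the 28-to-56-day range needs a cut-off that moves with the visit, whereas Section 8.3.1.6 sets it at the end of Week 6. Both points are right. These figures give scale and are not estimates of bias.

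Finally, endpoint derivation can be left to the analysis plan. That holds for detail, but here the protocol itself states collection windows that conflict.

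**Conclusion.** The concern holds and should be fixed. That the collection windows contradict one another is certain from the current text. The bias is conditional: zero if the endpoint is limited to the 21-day events or to a window ending at Week 6; zero or upward if it runs 12 weeks and sites follow the Week 6 rule. Its size cannot be derived because no late-event rate is given, and with dosing over by Day 7 it is probably modest. The firm figures are 42 of 84 days (50%) without full collection and 2.5 points per misclassified subject at n = 40.

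**What to change.** Reconcile the synopsis (Safety Assessments), footnote t of the schedule and Sections 8.3.1.6, 10.6 and 10.9 to one collection window that covers the primary endpoint. Possible wording:

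> Every AE of Grade 3 or above, whether serious or not, is entered in the CRF up to and including the Week 12 visit, with its relationship to investigational product and the start date of any new anticancer therapy.

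The therapy date lets toxicity of chemotherapy resumed before Week 12, which Section 3.1 allows, be separated from toxicity of the study product. Sections 7 and 8.4.9 already collect new anticancer therapy.

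If Week 6 is the intended limit, restate the endpoint window to match it.

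In either case, Section 12.4.2 should say which Grade 3 or higher events count for the primary endpoint (all, related, or related and treatment-refractory) and over what period. That period should replace the reference to one defined earlier.

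The cost is amendment wording and whatever additional AE entries arise in Weeks 6 to 12, a number the documents do not allow to be estimated. The Week 12 visit already lists adverse events and new anticancer therapies, so no visit or procedure is added.

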#### **8.3.1.7      Clinical Laboratory Assessments**

The hematology panel comprises a complete blood count (CBC), including white blood cell (WBC) count with differential, red blood cell (RBC) count, hematocrit, hemoglobin, red blood cell indices (MCV, MCH, MCHC), and platelet count.

The serum chemistry panel comprises the following parameters: aspartate aminotransferase (AST), alanine aminotransferase (ALT), lactate dehydrogenase (LDH), alkaline phosphatase (ALP), creatinine, total bilirubin, total protein, albumin, blood urea nitrogen (BUN), glucose, sodium, potassium, chloride, calcium, phosphorus, and bicarbonate (as CO2).

The coagulation panel includes aPTT and the INR.

The urinalysis panel (dipstick) includes appearance, pH, specific gravity, glucose, protein/albumin, presence of blood, ketones, bilirubin, nitrates, and leukocyte esterase. In addition, a microscopic exam for casts, crystals, and cells may be done if clinically indicated.

#### **8.3.1.8      Imaging Studies**

Subjects must consent to allow ZIOPHARM to collect their scan and tumor measurements that were taken a) prior to starting the pre-study standard chemotherapy, and b) prior to study entry, i.e., at the end of a minimum of 12 weeks of pre-study chemotherapy. Tumor response imaging for the pre-study standard chemotherapy must be completed within 4 weeks of study enrollment and must meet the criteria listed below in order to be used as screening/baseline scans. In the event that the scans are not adequate, they should be repeated.

- i. Computed tomography (CT) of the chest, abdomen +/- pelvis
- ii. PET or Bone Scintigraphy (BS) at the treating physician's discretion
- iii. MRI or CT of the brain, if brain metastasis are known or suspected
- iv. MRI of other anatomical regions as clinically indicated

All imaging should be of diagnostic quality and include intravenous (IV) contrast. Please refer to Appendix 16.3 for RECIST v 1.1 guidelines. NOTE: In the event that IV contrast cannot be used, the medical monitor should be consulted.

The same imaging method used for screening/baseline scans should be used for the tumor assessment performed at 6 and 12 weeks for the primary assessment of efficacy. Scans should be available for collection upon Sponsor request.

#### 8.3.1.9        Electrocardiogram

A standard 12-lead ECG for evaluation of the QT/QTc interval will be performed at screening.

### **8.4      List of Assessments by Study Period**

#### **8.4.1      Screening**

The screening exams, tests and procedures must be done within 28 days of Ad-RTS-hIL-12 injection.

- Signed Informed Consent Form
- Medical/Cancer History, including history of prior treatments and any associated residual toxicity
- Physical Examination
- ECOG performance status
- Height and weight
- Vital signs
- Adverse events
- Concomitant medications, i.e., medications taken within 28 days of Ad-RTS-hIL-12 injection
- Serum pregnancy test
- Hematology panel: CBC, WBC count with differential, RBC count, hematocrit, hemoglobin, red blood cell indices (MCV, MCG, MCHC), and platelet count
- Coagulation panel: aPTT and INR
- Serum chemistry panel: AST, ALT, LDH, ALP, creatinine, total bilirubin, total protein, albumin, BUN, glucose, sodium, potassium, chloride, calcium, phosphorus, and bicarbonate (as CO2)
- Screening hepatitis B, hepatitis C, and HIV serology in subjects without documented negative results, or in subjects with known risk factors for infection
- Baseline TSH
- Tumor markers: CEA and Ca 15-3
- Research bloods: for cytokines and immune cell activation by flow cytometry
- Urinalysis panel: appearance, pH, specific gravity, glucose, protein/albumin, presence of blood, ketones, bilirubin, nitrates, and leukocyte esterase. In addition, a microscopic exam for casts, crystals, and cells may be done if clinically indicated
- ECG at screening

- Receipt of copies of tumor measurements and scans taken a) before the start of the pre-study standard chemotherapy and b) at after a minimum of 12 weeks of the pre-study chemotherapy. Tumor response imaging must be completed within 4 weeks of study enrollment.

#### ***8.4.2 Immunotherapy Cycle: Day 1 (Ad-RTS-hIL-12 injection)***

- Physical examination (symptom-directed)
- ECOG performance status
- Weight
- Vital signs
- Adverse events
- Concomitant medications
- Hematology panel
- Research bloods
- Urinalysis
- Urine pregnancy test
- Tumor biopsy (prior to injection of Ad-RTS-hIL-12)
- Oral veledimex 3 hours  $\pm$  3 hours before injection of Ad-RTS-hIL-12
- Ad-RTS-hIL-12 injection
- Veledimex dose compliance/subject diary
- Veledimex dispensed for the following 6 days (the first dose is to be given in clinic)

#### ***8.4.3 Immunotherapy Cycle: Day 2***

- Oral veledimex
- Veledimex dose compliance/subject diary

#### ***8.4.4 Immunotherapy Cycle: Day 3***

- ECOG performance status
- Vital signs
- Physical examination (symptom-directed)
- Adverse events
- Concomitant medications
- Hematology panel
- Research bloods
- Oral veledimex
- Veledimex dose compliance/subject diary

#### ***8.4.5 Immunotherapy Cycle: Day 4-7***

- Oral veledimex
- Veledimex dose compliance/subject diary

#### **8.4.6 *Immunotherapy Cycle: Day 8***

- ECOG performance status
- Vital signs
- Physical examination (symptom-directed)
- Adverse events
- Concomitant medications
- Hematology panel
- Coagulation panel
- Serum chemistry panel
- Research bloods
- Collect veledimex dose compliance/subject diary

#### **8.4.7 *Immunotherapy Cycle: Day 21***

- Adverse events
- Concomitant medications

